6.3.11 Remote Contact

Sites will contact participants per the [SOE](#). Participants in the pre-selected site subset will have an in-person visit, instead of a remote visit on Days 0, 6, **and 20**, but will be contacted by telephone for that visit if they fail to attend the in-person visit. Refer to the A5395 MOPS for the remote contact script. Remote contact **attempts** will be recorded on the eCRF.

6.3.12 Study Endpoint Determination

Study endpoints will be collected per the [SOE](#) and outlined in [section 10.2](#). These will be recorded on the eCRF. Information about AEs, hospitalizations or death should be keyed on the eCRF within 72 hours of a site becoming aware of an AE, hospitalization or death.

6.3.13 Vital Status Follow-up

Site personnel should attempt to obtain information regarding vital status (including date last seen alive, hospitalization, date of death, and primary cause of death) **from the participant or other sources (such as family members, other designated contacts, hospital the participant stated they would most likely go to, clinic/hospital/medical records, and local or national databases)**, per the [SOE](#). Please see MOPS for additional information. Information about hospitalizations and deaths should be keyed on the eCRF within 72 hours of a site becoming aware of a hospitalization or death.

6.3.14 Household Linkage

At each site, at completion of the Day 20 visit for the last participant enrolled in the study at the site, the site will review all home addresses of A5395 participants to identify participants who live at the same address. The Household Linkage eCRF will be completed, and “linked” participant IDs recorded.

6.3.15 Virologic Studies

Self-Collected Dry Swabs

At pre-selected sites, a subset of participants may opt to self-collect Dry Swabs (nasal swabs) per the [SOE](#). Participants will be instructed by study staff and will obtain the swab while observed by study personnel. Additional information can be found in the MOPS and the LPC. At study entry (Day 0), the sample should be collected prior to the first dose of study treatment.

Nasopharyngeal (NP) Swab

At pre-selected sites, a subset of participants may opt to have an NP swab per the [SOE](#). Additional information can be found in the MOPS and the LPC. At study entry (Day 0), the sample should be collected prior to the first dose of study treatment.

Samples collected for viral assessment may be evaluated for the emergence of antiviral resistance at a future date.

6.3.15 Laboratory Evaluations

Laboratory evaluations will be performed on some participants at pre-selected sites. At study entry (Day 0), blood samples should be collected prior to the first dose of study treatment.

Hematology

Per the [SOE](#), participants will have the option to have a blood draw for complete blood cell count (CBC) with automated differential and platelet count. These tests will be performed in real-time at the local clinic laboratory.

Chemistry

Per the [SOE](#), participants will have the option to have a blood draw for liver function tests (ALT, ALP, AST, Total Bilirubin, Direct Bilirubin, and Total Protein) and renal function tests (BUN, Creatinine, Potassium, Glucose, and Sodium). A CrCl will be calculated and recorded by Cockcroft-Gault equation ([see Cockcroft-Gault calculator on the A5395 PSWP](#)). These tests will be performed in real-time at the local clinic laboratory.

Inflammatory Markers

Per the [SOE](#), participants will have the option to have a blood draw for lactate dehydrogenase, C-reactive protein, ferritin and D-dimer. These tests will be performed in real-time at the local clinic laboratory.

Stored Plasma

Per the [SOE](#), blood plasma will be collected and stored for future testing for immune responses and drug levels.

Stored Sera

Per the [SOE](#), blood sera will be collected and stored for future testing for immune responses and to compare antibody levels between treatment and control samples.

6.3.16 Pharmacokinetics

Per the [SOE](#), single sparse PK sampling will be collected. This will be done on a subset of participants who opt to have their blood drawn. Days 6 and 20 blood collection may be used to measure drug levels to assess drug adherence or surreptitious use of HCQ or Azithro.

7.0 ADVERSE EVENTS AND STUDY MONITORING

7.1 Definition of Adverse Events

An AE is any unfavorable and unintended sign (including an abnormal laboratory finding), symptom, or diagnosis that occurs in a study participant during the conduct of the study REGARDLESS of the attribution (i.e., relationship of event to medical treatment/study product/device or procedure/intervention). This includes any occurrence that is new in onset or aggravated in severity or frequency from the baseline condition.

7.2 Adverse Event Collection Requirements for This Protocol

Post-entry, all AEs must be recorded on the eCRFs within 72 hours if any of the following criteria have been met:

- All Grade ≥ 3 AEs
- All cardiac AEs regardless of grade
- All AEs that led to a change in study treatment/intervention regardless of grade
- All AEs meeting SAE definition or EAE reporting requirement

NOTE: SAEs or events meeting EAE reporting requirements should also be entered into the DAIDS Adverse Experience Reporting System (DAERS), an Internet-based reporting system.

All AEs that are reported must have their severity graded. To grade AEs, sites must refer to the DAIDS AE Grading Table, corrected Version 2.1, July 2017, which can be found on the DAIDS RSC website at <https://rsc.niaid.nih.gov/clinical-research-sites/daims-adverse-event-grading-tables>.

Serious Adverse Events (SAEs)

An SAE is defined as any untoward medical occurrence that:

- Results in death
- Is life-threatening illness
- Requires inpatient hospitalization or prolongation of existing hospitalization
- Results in persistent or significant disability/incapacity
- Is a congenital anomaly/birth defect.
- Is an important medical event that may not be immediately life-threatening or result in death or hospitalization but may jeopardize the patient or may require intervention to prevent one of the other outcomes listed in the definition above).

Ventricular arrhythmias, cardiac events requiring intervention or hospitalization, and deaths should be reported as soon as possible but no later than 24 hours to the A5395 Clinical Management Committee (CMC; e-mail: [contact]). If known, sites should indicate if the death was a sudden cardiac death. Sudden cardiac death is defined in this study as unexpected death from a cardiac cause within 1 hour of onset of symptoms OR found dead without clear explanation.

7.3 Expedited Adverse Event (EAE) Reporting to DAIDS

7.3.1 Expedited Reporting of Adverse Events to DAIDS

Requirements, definitions and methods for expedited reporting of Adverse Events (AEs) are outlined in Version 2.0 of the DAIDS EAE Manual, which is available on the RSC website at <https://rsc.niaid.nih.gov/clinical-research-sites/manual-expedited-reporting-adverse-events-daims>.

The DAIDS Adverse Experience Reporting System (DAERS), an Internet-based reporting system, must be used for EAE reporting to DAIDS. In the event of system outages or technical difficulties, EAEs may be submitted using the DAIDS EAE Form. This form is available on the DAIDS RSC website at <https://rsc.niaid.nih.gov/clinical-research-sites/paper-eae-reporting>.

For questions about DAERS, please contact NIAID CRMS Support at [contact]. Please note that site queries may also be sent from within the DAERS application itself.

For questions about expedited reporting, please contact the DAIDS RSC Safety Office at [contact].

7.3.2 Reporting Requirements for this Study

- The SAE Reporting Category, as defined in Version 2.0 of the DAIDS EAE Manual, will be used for this study.
- The study agents for which expedited reporting are required are:
 - HCQ or Placebo for HCQ
 - Azithro or Placebo for Azithro
- In addition to SAEs, other AEs that must be reported in an expedited manner are: all ventricular arrhythmias, and cardiac events requiring hospitalization or intervention

7.3.3 Grading Severity of Events

The DAIDS AE Grading Table, corrected Version 2.1, July 2017, must be used and is available on the DAIDS RSC website at <https://rsc.niaid.nih.gov/clinical-research-sites/daids-adverse-event-grading-tables>.

7.3.4 Expedited AE Reporting Period

- The expedited AE reporting period for this study is Day 0 (post first dose of study treatment, not including entry pre-treatment assessments) to Day 20.
- After the protocol-defined EAE reporting period (i.e., after Day 20, such as at remote visits at Weeks 12 and 24), unless otherwise noted, only suspected, *unexpected* serious adverse reactions (SUSARs), as defined in Version 2.0 of the DAIDS EAE Manual, will be reported to DAIDS if the study staff become aware of the events on a passive basis (from publicly available information).
- Any medical condition that is present at the time that the participant is screened will be considered as baseline and not reported as an AE. However, if the severity of any pre-existing medical condition increases to severity level 3 or 4 after starting study treatment, it should be recorded as an AE.

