10.2.2 Secondary Outcome Measures

- 10.2.2.1 Death from any cause during the 21-day period from and including the day of the first (confirmed) dose of study treatment.
- 10.2.2.2 Death from any cause or hospitalization or urgent visit to an emergency room or clinic during the 21-day period from and including the day of the first (confirmed) dose of study treatment.
- 10.2.2.3 Death from any cause or hospitalization during the 24-week period from and including the day of the first (confirmed) dose of study treatment. Hospitalization is defined as requiring at least 24 hours of acute care in a hospital or similar acute care facility, including Emergency Rooms or temporary facilities instituted to address needs during the COVID-19 pandemic. Evaluation at a hospital or similar facility with less than 24 hours of acute care is not considered a hospitalization.
- 10.2.2.4 Premature discontinuation of study treatment due to an adverse event.
- 10.2.2.5 Occurrence of any cardiac adverse events from start of study treatment through Day 20.
- 10.2.2.6 Duration of fever defined as the last day in the participant's daily diary card on which a temperature greater than 100.4°F was recorded or a potentially antipyretic drug, such as acetaminophen or ibuprofen, was taken.
- 10.2.2.7 Duration of symptoms associated with COVID-19 disease defined as the last day in the participant's daily diary card on which a moderate or worse symptom was recorded. The set of targeted symptoms are the same ones that are used in many influenza studies, with the addition of the symptoms of loss of smell and loss of taste, which have been associated with COVID-19 infection. The symptoms from influenza studies are: cough, shortness of breath, feeling feverish, fatigue, muscle aches, diarrhea, vomiting, nausea, headache, sore throat, nasal obstruction (stuffy nose), and nasal discharge (runny nose). These symptoms are listed individually on the Study Diary that each participant will complete each day. The scoring is that used in influenza studies, whereby participants grade each symptom as absent (score 0), mild (1), moderate (2), or severe (3).
- 10.2.2.8 **Participant-specific area under the curve (AUC) of the symptom**

score associated with COVID-19 disease **over time (through Day 20)** defined as the sum of scores for the targeted symptoms (defined above) in the participant's daily diary record (each individual symptom is scored from 0 to 3).

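### Section 7.3.4's grade 3–4 threshold for worsening of pre-existing conditions conflicts with the AE definition in 7.1 and the any-grade recording rules in 7.2

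*Protocol*

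**What the plan says.** Four places in the protocol bear on whether worsening of a condition present at screening is an AE.

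- **Section 7.1 (definition).** An AE includes any occurrence "new in onset or aggravated in severity or frequency from the baseline condition". There is no grade threshold.
- **Section 7.2 (collection).** "Post-entry, all AEs must be recorded on the eCRFs within 72 hours if any of the following criteria have been met". Two of the criteria ignore grade: "All cardiac AEs regardless of grade" and "All AEs that led to a change in study treatment/intervention regardless of grade".
- **Section 7.3.4 (expedited reporting period).** "Any medical condition that is present at the time that the participant is screened will be considered as baseline and not reported as an AE". The one stated exception is a pre-existing condition whose severity "increases to severity level 3 or 4 after starting study treatment, it should be recorded as an AE".
- **Section 10.2.2 (outcomes).** Outcome 10.2.2.5 is "Occurrence of any cardiac adverse events from start of study treatment through Day 20", with no grade limit. Outcome 10.2.2.4 is early stopping of study treatment because of an AE. Section 10.6.2 compares both between arms by binary regression adjusted for risk stratum.

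**The concern.** A participant enters with a known condition, and it gets worse after the first dose without reaching grade 3. Under 7.1 this is an AE. If it is cardiac, or if it leads to a change in study treatment, 7.2 requires it on the eCRF within 72 hours. Under 7.3.4 it is not an AE at all. No text says which rule prevails.

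Both outcomes at stake serve secondary objective 1.3.1, which names AEs leading to early discontinuation and cardiac AEs. The trial does no EKGs (section 2.1) and no physical examinations (section 6.3.6), and AEs are assessed mainly by remote contact (section 8.1). Cardiac safety therefore rests on what participants report and sites record, and the any-grade rule in 7.2 protects that record. If some sites follow 7.2 and others 7.3.4, the same event counts at one site and not at another.

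**Working it through.** **Step 1. Apply each rule to the same event.** The protocol states no figure to reproduce, so the check is a comparison of text.

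| Event after first dose | 7.1 and 7.2 | 7.3.4 as worded |
|---|---|---|
| New-onset cardiac event, any grade | Recorded | Not affected |
| Pre-existing condition worsens to grade 3 or 4 | Recorded | Recorded |
| Pre-existing cardiac condition worsens within grades 1–2, or only in frequency | Recorded | Not an AE |
| Pre-existing condition worsens within grades 1–2 and study treatment is changed | Recorded | Not an AE |

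The rules disagree only in the last two rows. The third row feeds outcome 10.2.2.5 and the fourth feeds 10.2.2.4. The count under 7.3.4 can only be equal to or lower than the count under 7.2.

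**Step 2. Does the placement of the sentence settle it?** Section 7.3 is about expedited reporting to DAIDS, but two features do not fit that scope.

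- The bullet just before it speaks of reporting to DAIDS. This one speaks of what is reported or recorded as an AE, which is the subject of 7.1 and 7.2.
- Section 7.3.2 triggers expedited reports by the SAE category, plus ventricular arrhythmias and cardiac events needing hospitalization or intervention. Severity grade is not a trigger there. A grade 3–4 threshold resembles the grade ≥ 3 criterion in 7.2.

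**Step 3. Can the last two rows occur?**

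- *Cardiac.* Section 4.2 excludes ventricular arrhythmia, antiarrhythmic use within 30 days, long QT syndrome, and ischemic or structural heart disease. It does not exclude other arrhythmias in people not taking antiarrhythmics. The group is narrow but not shown to be empty.
- *Treatment change.* Sections 8.2 and 8.3 say grade 1–2 events require no change, yet let the investigator stop treatment for an intolerable effect. Stopping for a low-grade worsening is therefore possible. Section 6.3.6 has the discontinuation and its reason recorded in any case, so what is in doubt is whether it is classed as due to an AE.

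**Step 4. Size.** The protocol gives no cardiac AE rate, no prevalence of pre-existing cardiac conditions and no power for this outcome, so the loss cannot be calculated. The following is illustration only. The only input from the protocol is about 1000 participants per arm (section 10.4). The event proportions and the shares unrecorded are assumptions.

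Let a share f of cardiac AEs go unrecorded equally in both arms, so that a = p0(1 − f) and b = p1(1 − f), with mean m = (a + b)/2 and n = 1000. For a two-sided 5% test,

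power = Φ{[(b − a) − 1.96·√(2m(1 − m)/n)] / √[(a(1 − a) + b(1 − b))/n]}.

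For 2% vs 4% and f = 0: (0.02 − 1.96 × 0.00763)/0.00762 = 0.66, and Φ(0.66) is about 0.746.

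| Assumed true proportions | f = 0 | f = 10% | f = 25% | f = 50% |
|---|---|---|---|---|
| 1% vs 2% | 45.2% | 41.4% | 35.6% | 25.3% |
| 2% vs 4% | 74.6% | 70.0% | 61.9% | 45.2% |
| 3% vs 5% | 62.7% | 58.0% | 50.2% | 35.8% |

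At 2% vs 4% the expected counts fall from 20 and 40 to 18 and 36 when f is 10%. Given the exclusions in Step 3, the larger values of f are hard to credit. The table shows direction and rough scale, not an estimate for this trial.

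**The case against.** The best defence is that the protocol already shows which section governs. Section 7.2 carries the collection requirements in its title, section 6.3.6 sends sites there for AE collection, and the disputed sentence sits among bullets about expedited reporting. The defence adds that 7.3.4 never says lesser worsening is exempt from 7.2, and that a rule specific to cardiac events should override a general one. This has weight: a careful site could well apply 7.2. It does not remove the conflict. The sentence first says the condition is not an AE and then makes a single exception, so the restrictive reading is the natural one, and it contradicts 7.1 as well as 7.2.

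Three further objections limit the point, and they stand.

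- A reader might infer that events are lost in the participants at greatest cardiac risk. Section 4.2 excludes most people with relevant heart disease. Cardiovascular disease as a stratum criterion, or arrhythmia as a medical-history item, does not show that such people are enrolled: the history list also includes coronary heart disease.
- A reader might extend 7.3.4 to symptoms present at screening, such as palpitations. The sentence speaks of a medical condition, and section 6.3.4 lists signs and symptoms apart from diagnoses. Whether symptoms fall under it is unclear.
- The most serious events have other routes. Ventricular arrhythmias and cardiac events needing intervention or hospitalization have their own reporting rules (7.2, 7.3.2), and torsades de pointes, ventricular arrhythmias and sudden deaths go to the DSMB (10.5).

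**Conclusion.** The conflict is real and stands in the current text. Under-counting of outcomes 10.2.2.4 and 10.2.2.5 is conditional: it arises at sites that apply 7.3.4 to the eCRF and not at sites that follow 7.2. The loss is confined to grade 1–2 worsening, or worsening in frequency only, of conditions present at screening. Its size cannot be derived from the protocol and is probably small for cardiac events.

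A reader might go further and conclude that the cardiac comparison is biased, or that a few lost events would change its result. The protocol does not support either. Recording is done under double blinding, so the omission does not favour an arm by design, and no event rate is given from which a changed result could be shown. What can be expected is somewhat lower counts, some loss of power and possible variation between sites. The correction is worth making because it costs almost nothing and removes a written rule that drops events from two named safety outcomes.

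**What to change.** Reconcile sections 7.1, 7.2 and 7.3.4. Limit the pre-existing-condition sentence in 7.3.4 to expedited reporting to DAIDS, and state that 7.1 and 7.2 govern eCRF recording. Any-grade worsening of a pre-existing condition after the first dose is then recorded when it is cardiac or leads to a change in study treatment.

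An exception for cardiac conditions alone would not be enough. It would leave the same conflict for AEs that change study treatment, and with the definition in 7.1.

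The cost is one sentence in the protocol and a few extra eCRF entries. No outcome, analysis or sample size changes.

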7.4 Study Monitoring

7.4.1 Adverse Events

The DAIDS Clinical Representative will review and assess select EAE reports for potential impact on the study participant safety and protocol conduct as per DAIDS policies, guidance documents, and SOPs as applicable. The A5395 protocol chair, vice chairs, and DAIDS Clinical Representative will review all deaths on a weekly basis in a blinded fashion.

7.4.2 Interim Review

The protocol team will monitor the conduct of the study via regular summaries of screening, accrual, study and study treatment discontinuation, and data and specimen completeness. An independent Data and Safety Monitoring Board (DSMB) will monitor safety regularly (see [section 10.5](#) for details.)

Detailed plans for study monitoring are outlined in a Study Progress, Data, and Safety Monitoring Plan (SPDSMP) developed by the Statistical and Data Management Center (SDMC) prior to enrollment of the first participant.

8.0 CLINICAL MANAGEMENT ISSUES

8.1 Toxicity

Criteria for participant management, dose adjustments and discontinuation, or changes in treatment will be described only for toxicities attributable to the study drugs (HCQ and Azithro). The grading system for drug toxicities is located in the DAIDS AE Grading Table (see [section 7.2](#)).

NOTE: The team must be notified via e-mail within 72 hours regarding toxicities that result in a change in study regimen ([contact]).

It is possible that some participants will experience transient or prolonged AEs during the study. However, it is important to note that, in this trial, the majority of visits will be conducted remotely and hence, AEs will be assessed remotely and unplanned study visits scheduled if deemed necessary by the site investigator. For any concerning AEs that are felt to require clinical intervention, participants should be instructed to contact their health care provider or seek urgent or emergent care, or 911 should be called, as appropriate.

Treatment may be discontinued without contacting the CMC in advance, but the study team should be notified via email within 72 hours of treatment discontinuation, as described above.

8.2 Management of Side Effects of HCQ [78]

Gastrointestinal effects

Gastrointestinal (GI) symptoms including nausea, vomiting, and diarrhea are common with HCQ. HCQ should be administered with food or milk. In the event of GI symptoms, the study staff should review with the participant if HCQ is being taken with food, as administration of HCQ with food may reduce GI effects. GI side effects do not require treatment discontinuation and participants may be referred to their health care provider for symptomatic treatment (e.g., antiemetics). However, in the event of any treatment-related toxicity (GI or other), the site investigator has the option to discontinue study treatment if the side effect is intolerable or at their discretion.

Rash

A range of dermatologic reactions may be observed with HCQ. For pruritus, emollients may be used. For other more significant reactions, such as potential allergic skin reactions, HCQ should be discontinued immediately, and the participant referred to their health care provider or for urgent evaluation and management as appropriate, as determined by the site investigator. Over-the-counter topical agents may be recommended by the site clinical investigator, if the investigator feels able to make such a recommendation.

Hypoglycemia

Severe hypoglycemia (i.e., hypoglycemia that requires intervention) may occur with HCQ. HCQ should be discontinued immediately in participants who develop severe hypoglycemia.

Cardiovascular effects

Cardiomyopathy, QT prolongation, and ventricular arrhythmias have been reported with HCQ use. HCQ should be discontinued immediately in participants who experience a cardiovascular event, and additional evaluation and management pursued as appropriate for the clinical condition, as determined by the site investigator.

In the event of any treatment-related toxicity, the site investigator has the option to discontinue study treatment if treatment is intolerable or at the investigator's discretion. Treatment may be discontinued without contacting the A5395 clinical management committee (CMC) in advance, but the study team should be notified via email within 72 hours of treatment discontinuation, as described above.

Dose modification of HCQ will not be allowed in the study. If HCQ/Placebo is discontinued for toxicity reasons, all study medications should be discontinued and not be restarted.

NOTE: Grades 1 and 2 AEs associated with HCQ require no change in study treatment.

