8.3 Management of Side Effects of Azithro [79]

Hypersensitivity reactions

Allergic reactions such as angioedema, anaphylaxis, Stevens-Johnson syndrome, toxic epidermal necrolysis, and DRESS have been reported rarely with azithromycin

administration. Azithromycin should be discontinued immediately in the event of a hypersensitivity reaction.

Cardiovascular events and altered cardiac conduction

Macrolides have been associated with rare QT prolongation and ventricular arrhythmias but not Azithro in clinical studies (see Rationale above). Some studies, but not all, have described an association between azithromycin and cardiovascular events and mortality [41]. Therefore, to be conservative, Azithro should be discontinued immediately in the event of a cardiovascular event and additional evaluation and management pursued as appropriate for the clinical condition, as determined by the site investigator.

GI symptoms including diarrhea, nausea, and vomiting occur frequently (>10%) in azithromycin recipients. Azithro may be administered with food to reduce GI side effects. GI side effects do not require treatment discontinuation and participants may be referred to their health care provider for symptomatic treatment (e.g., antiemetics). However, in the event of any treatment-related toxicity (GI or other), the site investigator has the option to discontinue study treatment if the side effect is intolerable or at their discretion.

Dose modification of Azithro will not be allowed in the study. If Azithro/Placebo is discontinued for toxicity reasons, all study medications should be discontinued and not be restarted.

NOTE: Grades 1 and 2 AEs associated with Azithro require no change in study treatment.

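### Sections 8.2 and 8.3 conflict on whether a drug-attributed grade 1–2 cardiovascular event requires stopping study treatment

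*Protocol*

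**What the plan says.** Protocol section 8.2, in its cardiovascular paragraph, orders: "HCQ should be discontinued immediately in participants who experience a cardiovascular event". Section 8.3 gives the matching order for azithromycin: "Therefore, to be conservative, Azithro should be discontinued immediately in the event of a cardiovascular event". Neither sentence names a grade, and the protocol does not define a cardiovascular event by severity.

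Each section then ends with a general line. Section 8.2 has "NOTE: Grades 1 and 2 AEs associated with HCQ require no change in study treatment" and section 8.3 has "NOTE: Grades 1 and 2 AEs associated with Azithro require no change in study treatment". Neither lists an exception.

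Four other provisions bear on how these fit together:

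- Section 8.1 limits all management criteria in section 8 to toxicities attributable to the study drugs and grades them on the DAIDS table.
- Section 8.2 leaves room for judgement on treatment-related toxicity: "the site investigator has the option to discontinue study treatment if treatment is intolerable", or at the investigator's discretion. Section 8.3 has a similar clause.
- A stop for toxicity is complete and permanent: "If HCQ/Placebo is discontinued for toxicity reasons, all study medications should be discontinued and not be restarted". Section 8.3 says the same for azithromycin.
- Section 9.1 refers drug-related toxicity back to section 8. It separately requires a stop for an SAE at least possibly related to study drug and for reasons believed life-threatening.

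**The concern.** A site that learns of a mild, drug-attributed cardiovascular event finds one sentence telling it to stop at once and another telling it that no change is needed. Nothing says which governs.

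This matters more here than in most trials. Cardiac toxicity is the leading safety concern for this combination: cardiac AEs are part of a secondary objective and are a secondary outcome. Section 2.1 explains why no EKG is done at screening or during treatment, section 2.2 rejects mobile ECG monitoring, and section 8.1 says AEs will be assessed remotely because most visits are remote. Site staff therefore lean heavily on the written rule. A site that follows the NOTE could keep dosing after an event for which the paragraph above it orders a stop.

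The other safeguards are aimed at serious events. Section 9.1 acts on related SAEs and life-threatening reasons. The 24-hour report in section 7.2 covers ventricular arrhythmias, cardiac events needing intervention or hospital care, and deaths. The DSMB notice in section 10.5 covers TdP, ventricular arrhythmias and sudden deaths. A mild event is left to the two section 8 rules and the investigator's discretion.

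**Working it through.** **Do the two rules meet in the same case?** Take a cardiovascular event of grade 1 or 2 that the investigator attributes to HCQ.

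1. Section 8.1 confines section 8 to drug-attributed toxicity, so both the cardiovascular paragraph and the NOTE apply.
2. The paragraph says stop; the NOTE says no change is required.
3. Section 9.1 points back to section 8 and sets no precedence.
4. Low-grade cardiac events are foreseen, because section 7.2 has sites record cardiac AEs of every grade.
5. Where the protocol wants a severity limit it writes one. Section 8.2 restricts the hypoglycemia stop to severe hypoglycemia, and section 7.2 restricts the 24-hour report to cardiac events needing intervention or hospitalization. The cardiovascular stop has no such limit.

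The conflict is therefore on the page, in both sections.

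**Do the other stop orders share it?** The section 8.3 order "Azithromycin should be discontinued immediately in the event of a hypersensitivity reaction" also carries no grade and has the same form. It is a side point, because most of the reactions listed there are severe. The section 8.2 rash rule differs: pruritus gets emollients, and the stop has its own threshold, "For other more significant reactions, such as potential allergic skin reactions, HCQ should be discontinued immediately". That rule is workable as written.

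**How much exposure depends on the reading?** The documents state no figure, so it is derived from the regimen in section 5.1.

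- HCQ total: 2 × 400 + 12 × 200 = 3200 mg, which agrees with section 2.1.
- Azithromycin total: 500 + 4 × 250 = 1500 mg.
- Remaining dose = total − dose taken so far. Because a toxicity stop ends both drugs, both remainders are at stake.

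| Point in the course | HCQ left | Azithromycin left |
|---|---|---|
| After the first doses | 3200 − 400 = 2800 mg (87.5%) | 1500 − 500 = 1000 mg (67%) |
| After Day 2 doses | 3200 − (800 + 2 × 400) = 1600 mg (50%) | 1500 − (500 + 2 × 250) = 500 mg (33%) |
| After Day 4 doses | 3200 − (800 + 4 × 400) = 800 mg (25%) | 1500 − (500 + 4 × 250) = 0 |
| After Day 6 doses | 3200 − (800 + 6 × 400) = 0 | 0 |

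The last three rows assume that both loading doses fall on Day 0. Section 6.3.10 notes that some participants finish HCQ on Day 7. If the second loading dose slips to Day 1 and later doses shift with it, one 200 mg capsule more is outstanding at the end of each day: 1800 mg after Day 2, 1000 mg after Day 4 and 200 mg after Day 6. Contact windows in section 6.1 also make Days 2 and 4 reference points rather than fixed times.

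These amounts apply to the active arm. Of the planned 2000 participants, about 1000 receive placebo and have no drug exposure at stake.

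**The case against.** The best counter-argument is that ordinary reading mostly settles the matter. Severity limits in section 8.2 sit inside the specific paragraphs, and the cardiovascular paragraph sets none. Section 8.3 gives its stop as a conservative measure. The NOTE follows the dose-modification text and can be read as a default for effects without their own rule. A general default does not naturally cancel a specific order to stop. This has force: the specific paragraph is the more natural rule to govern. But the protocol does not say so. The NOTE comes last, is specific to grade and exempts nothing, so a site could equally read it as limiting the paragraphs above to grade 3 and higher.

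A reader might infer that the NOTE tells sites to continue dosing. It does not. Requiring no change is not forbidding one. A site that stops for a mild cardiovascular event complies with every sentence, and section 8.1 lets it do so without contacting the clinical management committee in advance. What is open is only whether the stop is mandatory.

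A reader might also infer that serious cardiac events are left unprotected. They are not, given sections 7.2, 9.1 and 10.5.

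The affected group is narrow: the event must be cardiovascular, drug-attributed, grade 1–2, reported while doses remain, and not stopped at discretion. Without EKGs, mild QT change will seldom be found. Section 2.2 adds that, given the long half-lives and short course, stopping after QTc prolongation may achieve little. All of this stands. It limits the size of the point without removing the contradiction.

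Finally, because a cardiovascular event is undefined, a firm stop rule could end both drugs for mild, subjective palpitations. That is a fair cost, but it already follows from the stop orders as written.

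**Conclusion.** The point holds in a limited form. Sections 8.2 and 8.3 are internally inconsistent on whether a drug-attributed grade 1–2 cardiovascular event requires a stop. The wording should be corrected because it is a safety stop rule in a trial without EKGs and with mostly remote AE assessment.

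For an active-arm participant, the treatment that turns on the reading runs from most of the course, if the event follows the first doses, down to little or nothing by Day 6–7. This rests on the section 5.1 schedule being taken as written, apart from the Day 7 shift. The gain from a clear rule is less further exposure; the documents do not support expecting reversal of a QT effect.

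No number of affected participants can be given. The documents state no rate of mild cardiovascular events, and few are likely. Sample size and primary analysis are unaffected. Nor do the documents support extending the criticism to the rash rule, or concluding that a grade limit was intended: adding one would be a sponsor policy choice in the opposite direction to the stop orders.

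**What to change.** Add one clause to each closing NOTE:

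- Section 8.2: *except cardiovascular events, which are managed as stated above.*
- Section 8.3: *except cardiovascular events and hypersensitivity reactions, which are managed as stated above.*

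This keeps the protocol's own conservative stop orders and makes them govern. Leave the section 8.2 rash rule as it is.

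The cost is wording only, with no change to data collection, sample size or analysis. The downside is possibly a few more discontinuations for mild events, each ending all study medication without restart. Where they occur, they would count towards the secondary outcome of premature discontinuation due to an adverse event (section 10.2.2.4).
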